5.5.12 Reporting Urgent Safety Measures

In the event of a potential USM, the investigator must contact the Astellas Study Physician (within 24 hours of awareness). Full details of the potential USM are to be recorded in the subject's medical records. The sponsor may request additional information related to the event to support their evaluation.

If the event is confirmed to be an USM the sponsor will take appropriate action to ensure the safety and welfare of the subjects. These actions may include but are not limited to a change in study procedures or study treatment, halting further enrollment in the trial, or stopping the study in its entirety. The sponsor or sponsor's designee will notify CA and cEC within the timelines required per current local regulations, and will inform the investigators as required. When required, investigators must notify their IRB/IEC within timelines set by regional regulations.

5.6 Test Drug Concentration

Serum concentrations of ASP1650 will be measured. Samples will be collected as outlined in the ASP1650 Pharmacokinetic and Immunogenicity Schedule [Table 2]. Blood sampling, processing, storage and shipment instructions will be provided in the Laboratory Manual. Samples will be shipped to and analyzed by a sponsor-designated analytical laboratory using validated analytical methods. Samples remaining after pharmacokinetic assessments may be

used for additional biomarker analysis described in [Section 5.7.2 Exploratory Biomarker]. Please refer to the Laboratory Manual for more detailed information.

5.7 Other Measurements, Assessments or Methods

5.7.1 Optional Blood Sample for Banked Pharmacogenomic Sample Analysis

For subjects who signed a separate ICF, an optional whole blood sample for PGx will be collected at C1D1. PGx research may be conducted in the future to analyze or determine genes of relevance to clinical response, pharmacokinetics and toxicity/safety issues. A sample of whole blood for possible retrospective PGx analysis will be collected and processed. Blood sampling, processing, storage and shipment instructions will be provided in the Laboratory Manual. Samples will be shipped to a sponsor-designated analytical/storage laboratory. Please refer to the Laboratory Manual for more detailed information

See [Appendix 12.7 Pharmacogenomic (PGx) Analysis With Banked Sample (Optional)] for further details on the banking procedures.

5.7.2 Exploratory Biomarker

Tumor tissue and blood/serum/plasma samples described in [Sections 5.7.2.1 Blood, Plasma and Serum Samples and 5.7.2.2 Tumor Tissue Samples for Biomarker Analysis] may be used for research purposes to identify genomic and/or other biomarkers that may be associated with clinical outcome or dynamic changes associated with ASP1650 treatment (in terms of dose, safety, tolerability and efficacy).

Since the identification of exploratory biomarkers that correlate with the efficacy or safety of ASP1650 treatment may continue to evolve as new findings become available, additional analyses related to ASP1650 activity on tumor signaling pathways or clinical outcomes may be conducted. Tumor tissue and blood/serum samples remaining after the specified biomarker assessments (e.g., aliquots of tumor cell RNA or DNA) may be used for re-testing, additional analyses as defined above or developing, and validating assays related to prediction of response or dynamic changes associated with ASP1650 treatment.

The tumor tissue and blood/serum/plasma samples (e.g., aliquots of tumor cell RNA or DNA, peripheral blood mononuclear cells) will be stored at the study sponsors' facility or a contract laboratory facility for up to 15 years after database closure, at which time the samples will be destroyed. The procedures for the collection, handling and shipping of laboratory samples being submitted to the central laboratory will be specified in a laboratory manual.

5.7.2.1 Blood, Plasma and Serum Samples for Biomarker Analysis

Blood, serum and plasma samples will be collected according to the Schedule of Assessments [Table 1] for exploratory biomarker measurements. Blood, serum and plasma samples may be analyzed for biomarkers including but not limited to chemokines, cytokines, CDC activation, circulating DNA soluble factors and genetic markers.

5.7.2.2 Tumor Tissue Samples for Biomarker Analysis

Formalin fixed paraffin embedded tumor tissue samples will be obtained for all subjects during the screening period. Subjects must have an available tumor specimen in a tissue block or unstained serial slides, or subject must be an appropriate candidate for tumor biopsy and be amenable to undergoing a tumor biopsy during the screening period. If a biopsy is performed, collection from a site other than lymph nodes is preferred.

An optional on-treatment tumor specimen collected ± 7 days of the cycle 4/day 1 visit may be provided. In cases where a pretreatment biopsy was performed, collection of the on-treatment specimen from the same site is preferred.

The investigator, in consultation with other specialists, as needed (e.g., radiology staff) will assess the risk associated with obtaining a tumor tissue sample and determine if the subject is an appropriate candidate for the procedure. Biopsies should be obtained in accordance with institutional policies/guidelines to minimize risk. Procedures requiring general anesthesia should not be performed to obtain a tumor tissue sample; however, if a surgical procedure under general anesthesia is performed for a clinical indication, excess tumor tissue may be used for research purposes with the consent of the subject. If a tumor biopsy is to be obtained during screening from a lesion that will be classified as 1 of the target lesions, the biopsy should be performed prior to obtaining the baseline scan, if possible. Otherwise, a new baseline scan should be obtained subsequent to the biopsy of the target lesion.

Tumor tissue samples may be analyzed for biomarkers including but not limited to CLDN6 expression, immune cell infiltration, genetic markers and gene/protein expression related to the mechanisms of action of the study drug.

Tumor Tissue Requirements

Visit	Tumor Tissue Requirement
Screening	A minimum of 1 FFPE tumor tissue block with adequate viable tumor cells (preferred) OR a minimum of 9* FFPE unstained slides are required.
Post-Progression (optional)	A minimum of 1 FFPE tumor tissue block with adequate viable tumor cells (preferred) OR a minimum of 9* FFPE unstained slides are required.

FFPE: formalin-fixed paraffin embedded

*If ≥ 9 slides cannot be provided, the sponsor should be contacted for further guidance.

5.8 Total Amount of Blood

The total amount of blood collected for study assessments for each subject will vary depending on how long they stay on treatment.

At any time during the study, if any laboratory abnormalities are found for a subject or for disease assessment, additional blood may be drawn for monitoring.

Additional blood beyond standard monitoring that will be drawn for this study will include draws for eligibility assessment, hematology, chemistry, and coagulation at specific study defined time points, pharmacokinetics, and biomarker sampling.

The maximum amount of blood collected is approximately 67 mL in cycle 1. The amount collected in subsequent cycles is less.

6 DISCONTINUATION

6.1 Discontinuation of Individual Subject(s) From Study Treatment

The study treatment period is a maximum of 12 treatment cycles. A subject is free to withdraw from the study treatment and/or study for any reason and at any time without giving reason for doing so and without penalty or prejudice. The investigator is also free to terminate a subject's involvement in the study at any time if the subject's clinical condition warrants it.

The subject will be discontinued from study treatment if any of the following occur:

- Investigator determines it is in the subject's best interest to discontinue study treatment
- Subject develops disease progression based on serum tumor markers or radiological disease progression as assessed by the investigator.
 - If the investigator believes that the subject is continuing to derive clinical benefit (asymptomatic and/or without worsening of performance status or overall health) from study treatment, and an increase in tumor burden is not likely to affect vital organ function, the subject may remain on study treatment up to a maximum of 12 treatment cycles.
- Subject starts another systemic chemotherapy, immunotherapy, radiotherapy or other treatment intended for antitumor activity.
- Subject starts other investigational agent or device.
- Subject develops unacceptable toxicity.
- Subject has a delay of study treatment for ≥ 28 days from when the next study treatment was scheduled to be administered. However, restarting study treatment after dosing delay (beyond ≥ 28 days from when the next study treatment was scheduled to be administered) may be allowed based on investigator consultation with, and approval of, the Astellas medical monitor.
- Subject develops inter-current illness that the investigator determines may jeopardize the subject's safety if the subject continues to receive study treatment.
- Significant deviation from the protocol or eligibility criteria as determined by the sponsor.
- Subject declines further treatment.
- Subject is lost to follow-up despite reasonable efforts by the investigator to locate the subject.
- Subject is noncompliant with the protocol based on investigator or medical monitor assessment.

NOTE: If a subject discontinues ASP1650 prior to disease progression per modified RECIST v1.1 and is not receiving any other systemic anti-cancer therapy, the subject must continue to undergo radiological assessments per protocol-specified schedule.

Study Discontinuation Criteria

A subject will be discontinued from the study if any of the following occur:

- Subject or legally authorized representative specifically withdraws consent for any further contact.
- Subject is lost to follow-up despite reasonable efforts by the investigator to locate the subject.
- Death (from any cause).
- Study termination by the sponsor.

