Samples for pharmacokinetics, immunogenicity and biomarkers will be collected. An optional on treatment tumor tissue sample may be collected. Pharmacogenomics (PGx) and post-progression tumor samples may be collected for those subjects who sign separate informed consent forms (ICFs).

Follow-up Period

Following discontinuation from study treatment, subjects will have a Study Treatment Discontinuation Visit ≤ 7 days after their last dose of study drug or decision by the investigator to discontinue treatment, in addition to a Safety Follow-up visit at 30 days (+7 days) after their last dose of study drug.

If a subject discontinues study drug prior to radiologic progression, the subject should enter the Post-Treatment Follow-up Period. The subject should continue to undergo imaging assessments and serum AFP and serum βhCG every 6 weeks + 7 days counting from C1D1 for the first 24 weeks and then every 12 weeks ± 7 days thereafter until 1 of the following events occurs:

- Radiological disease progression
- Subject starts another anticancer treatment

All post-progression anti-cancer therapies including date and site of progression will be recorded on the electronic case report form (eCRF).

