5.1.3 Previous and Concomitant Treatment (Medication and Non-Medication Therapy)

Previous treatment is defined as medication and non-medication therapy (e.g., diet, sodium intake restriction, rehabilitation, etc.) undergone before entering the investigational period.

Prohibited Prior Treatment or Therapies

- Systemic immunosuppressive therapy, including systemic corticosteroids within 14 days prior to first dose of study treatment. Subject using a physiologic replacement dose of hydrocortisone or its equivalent (defined as up to 30 mg per day of hydrocortisone or up to 10 mg per day of prednisone) or a single dose of systemic corticosteroids is eligible. Subject who received systemic steroids for asymptomatic CNS metastases within 14 days prior to first dose of study treatment is eligible.
- Other investigational agents or devices within 28 days prior to first dose of study treatment.

- Prior anti-cancer mAb within 4 weeks prior to study day 1 or ongoing toxicity (i.e., > grade 1 or at baseline) from AE due to mAb agents administered more than 4 weeks earlier.
- Prior chemotherapy, targeted small molecule therapy, or radiation therapy within 2 weeks prior to study day 1 or ongoing toxicity (i.e., > grade 2 or at baseline) from AEs due to a previously administered agent

Concomitant treatment means medication and non-medication therapy (e.g., opioids, sodium intake restriction, rehabilitation, etc.) used during the investigational period.

All concomitant treatments will be recorded in the eCRF.

Prohibited Concomitant Treatment

The following are strictly prohibited:

- Systemic immunosuppressive agents:
 - Concurrent systemic immunosuppressive therapy, in particular systemic corticosteroids, must be stopped 14 days prior to first dose of study treatment. However, subjects are allowed to initiate use of systemic steroids for CNS metastases after the first dose of study treatment.
 - Subjects are allowed to use a physiologic replacement dose of hydrocortisone or its equivalent (defined as up to 30 mg per day of hydrocortisone or up to 10 mg per day of prednisone) or a single dose of systemic corticosteroids.
- Other systemic chemotherapy, immunotherapy, radiotherapy, herbal medications or other treatments intended for antitumor activity. Palliative radiotherapy for peripheral bone metastases is allowed.
- Investigational products or therapy other than ASP1650.

Cautionary Concomitant Treatment

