Considerations should be given to avoid or minimize the use of the following concomitant medications, if possible, during ASP1650 treatment:

- Systemic corticosteroids, because their impact on the potential efficacy of ASP1650 is not known.
 - Systemic corticosteroids should be avoided or minimized while subject is on study treatment unless required for management of an emergent medical condition (e.g., severe hypersensitivity reaction).
 - For a subject's first dose of ASP1650, it is recommended that the prophylactic use of corticosteroids be avoided.
 - Inhaled, intranasal and topically applied steroids are allowed.

Prohibited Non-drug Procedures

- Any surgery (including palliative) that involves removal of tumor/metastases masses that may affect the efficacy assessments (removal of small non-measurable masses may be allowed)

A list of excluded medications can be found in [Appendix [12.1](#) List of Excluded Concomitant Medications].

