7.1 Sample Size

The sample size for the Safety Lead-in phase is not based on a statistical power calculation. The planned number of up to 18 subjects would provide adequate information for the objectives of the safety cohort.

Simon's optimal 2-stage design [Simon, 1989] will be used for conducting phase 2 of the study. The null hypothesis is that the true ORR is 10%, and the alternative hypothesis is that the true ORR is 25%. The study will be carried out in 2 stages. In stage I, a total number of 13 subjects treated at the RP2D will be evaluated.

If there is 1 or fewer responses among these 13 subjects, the study will be stopped early for futility. Otherwise, an additional 21 subjects will be enrolled in stage II, resulting in a total number sample size of 34. If there are 6 or more responses among these 34 subjects, we reject the null hypothesis and claim that the treatment is promising. The design controls the type I error rate at 10% and yields the power of 80%.

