In subjects whose only evidence of disease is elevated serum tumor markers ($> 2 \times$ ULN AFP or $> 2 \times$ ULN β hCG) at baseline, the modified RECIST v1.1 will reduce to serum tumor marker response criteria. Serum marker criteria can be found in section 5.3.1.3 of the protocol. In subjects whose only evidence of disease is elevated serum tumor markers ($> 2 \times$ ULN AFP or $> 2 \times$ ULN β hCG) at baseline, confirmatory assessment for CR or PR is not required.

Best overall response is determined once all tumor response data for the subject is available. Subjects will be classified by best response on study as outlined in modified RECIST v1.1 criteria. For best overall response of stable disease (SD), SD must be documented as present at least once after study entry and maintained for at least 12 weeks.

ORR as assessed by RECIST 1.1 alone and by serum marker alone will be performed as a sensitivity analysis.

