5.2.3 Progression-Free Survival (PFS)

PFS is defined as the time from the date of first dose until the date of disease progression as assessed by modified RECIST 1.1, or until death due to any cause. If a subject has neither progressed nor died, the subject will be censored at the date of last disease assessment or at the date of registration if no post-baseline radiological assessment is available. Subjects who receive any further anticancer therapy for the disease before disease progression will be censored at the date of the last disease assessment before the anticancer therapy started. If progression or death occurs after missing 2 scheduled disease assessments, the subject will be censored at the date of last disease assessment or at the date of registration if no post-baseline disease assessment is available. A subject has missed 2 scheduled disease assessments if the gap between two disease assessments is more than 2.5 times the scheduled disease assessment interval. During treatment, this will be 105 days (2.5 x 42 days during treatment for the first 24 weeks); during the follow-up period this will be 210 days (2.5 x 84 days during follow-up).

PFS (in days) is calculated as:

(Date of death, or Progression assessed by modified RECIST 1.1, or censoring) – (Date of first dose) +1.

To apply the cut-off date to PFS is to exclude disease assessments, death and anti-cancer therapy date after cut-off date in the analysis.

Note: Patient cannot be censored at “Not Evaluable (NE)”. If NE is the only previous assessment, then PFS will be censored at Day 1.

PFS will be calculated for each subject using RECIST 1.1 alone, and serum markers alone.

Table 3 PFS Definition

Situation	Date of Event or Censor	Outcome
No evaluable post-baseline efficacy assessments, no death	Date of first dose	Censor
Subject did not receive new anti-cancer therapy:		
Disease progression documented per modified RECIST v1.1	Date of PD	Event
No disease progression, but death recorded on eCRF	Date of death	Event
No PD nor death	Date of last efficacy assessment or at the date of first dose if no postbaseline efficacy assessment is available	Censor
Subject received new anti-cancer (ACT) therapy:		
Disease progression documented per modified RECIST v1.1 after new ACT	Date of last efficacy assessment before start of new anti-cancer therapy or at the date of first dose if no post-baseline efficacy assessment is available	Censor

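### The rules for ending disease assessments conflict on local anticancer treatment, and best overall response, ORR, CBR and DOR have no cut at such treatment although PFS does

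*Protocol*

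**What the plan says.** The documents end disease assessments in two different ways.

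- **Radiological progression or other *systemic* anticancer treatment.** This is in the Protocol Synopsis and 2.2.1 (Safety Lead-in and Phase 2 Assessments), Table 1 footnotes 15 (imaging) and 20 (markers), 5.3.1.1, 5.3.1.3, and the corresponding assessment text in SAP 2.2.1.1. The NOTE in Protocol 6.1, repeated in the Synopsis, agrees. It covers a subject who stops ASP1650 before progression by modified RECIST v1.1 "and is not receiving any other systemic anti-cancer therapy, the subject must continue to undergo radiological assessments per protocol-specified schedule".
- **Radiological progression or *any* other anticancer treatment.** This is in the Follow-up Period text of the Protocol Synopsis, Protocol 2.2.1 and the SAP design section. The second stopping event there is "Subject starts another anticancer treatment", with no restriction to systemic therapy.

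On the endpoints:

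- SAP 5.1.1 states: "Best overall response is determined once all tumor response data for the subject is available". Neither SAP 5.1.1, SAP 6.4.1.2 nor Protocol 7.4.1.1 says what happens to assessments made after another anticancer treatment. SAP 6.4.1 places efficacy on the FAS, which is all enrolled subjects.
- SAP 5.2.1 (CBR) and 5.2.2 (DOR, Table 2) are equally silent.
- SAP 5.2.3 does have a rule for PFS: "Subjects who receive any further anticancer therapy for the disease before disease progression will be censored at the date of the last disease assessment" before that therapy began. Table 3 sets it out row by row.

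During treatment, Protocol 5.1.3 prohibits antitumor radiotherapy, and surgery that could disturb the efficacy assessments. There are two exceptions: "Palliative radiotherapy for peripheral bone metastases is allowed", and "removal of small non-measurable masses may be allowed". Protocol 6.1 makes starting radiotherapy or another antitumor treatment a reason to stop study drug.

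**The concern.** A single-arm ORR is read as the effect of the drug, so a response produced by another treatment biases it upward. Here a site that follows the NOTE in Protocol 6.1 can generate such a response while fully compliant, and no SAP rule takes it out. One subject could be censored in PFS before the other treatment and counted as a responder in ORR because of it.

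There is little behind the ORR rule to catch this. Excluded concomitant treatment is only tabulated, as deviation PD4. The per-protocol set that Protocol 7.2.2 and 7.4 offer as a robustness check does not appear in the SAP. Response is read by the local investigator in an open-label study.

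The decision thresholds are small counts: at least 2 of 13 to continue and at least 6 of 34 to claim activity. A single misattributed response can matter.

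**Working it through.** **1. Can the case arise under the text?** Take a subject with stable disease who stops ASP1650 without progression and then has an assessed lesion irradiated or resected.

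| Question | Systemic wording | Follow-up wording |
|---|---|---|
| Scans and markers continue? | Yes | No |
| Later confirmed CR/PR used in best overall response? | Yes, nothing excludes it | No scheduled assessment to use |
| PFS | Censored before the local treatment | Censored before the local treatment |

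The outcome depends on which section the site follows. The off-drug period is real: treatment is capped at 12 cycles × 14 days = 168 days = 24 weeks. The futility look comes 24 weeks after the 13th subject's first dose, so subjects enrolled earlier may by then have been off drug for some time.

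**2. Which local treatments can create a responder?** By Protocol Table 4 (SAP Table 1), target SD with non-target CR is SD. PR needs target PR or CR, apart from one row for subjects with no target lesion whose non-target disease is CR but a marker stays above the ULN. Markers need only not have risen by 50% or more; a fall does not lift target SD to PR. The route is therefore treatment of the target lesions themselves, mainly after study drug has stopped. The documents do not say how a resected target lesion is scored.

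**3. The plan's own figures.** Inputs from Protocol 7.1: null ORR 10%, alternative 25%, 13 subjects in stage I, 21 more in stage II, claim at 6 or more of 34. For stage I, "If there is 1 or fewer responses among these 13 subjects, the study will be stopped early for futility".

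- Early stop at p = 0.10: 0.9^13 + 13 × 0.1 × 0.9^12 = 0.2542 + 0.3672 = 0.621.
- P(reject) = Σ over x = 2 to 13 of Bin(x; 13, p) × P[Bin(21, p) ≥ 6 − x]. This is 0.0957 at p = 0.10 and 0.811 at p = 0.25.

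The stated 10% type I error and 80% power are reproduced.

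**4. Illustration: one subject counted as a responder because of other treatment.** All other subjects respond independently with probability 0.10.

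- In stage I: one response is given, so at least 1 of the other 12 is needed to continue. Early stop = 0.9^12 = 0.282. P(reject) = Σ over y = 1 to 12 of Bin(y; 12, 0.1) × P[Bin(21, 0.1) ≥ 5 − y] = 0.2156.
- In stage II: early stop is unchanged at 0.621. P(reject) = Σ over x = 2 to 13 of Bin(x; 13, 0.1) × P[Bin(20, 0.1) ≥ 5 − x] = 0.1705.

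**5. The same by rate.** The documents give no rate, so q, the share of true non-responders counted as responders, is an assumption. The apparent ORR is 0.10 + 0.90q.

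| q (assumed) | Apparent ORR | Type I error | Early stop |
|---|---|---|---|
| 0 | 0.100 | 0.096 | 0.621 |
| 1% | 0.109 | 0.130 | 0.578 |
| 2% | 0.118 | 0.169 | 0.536 |
| 3% | 0.127 | 0.213 | 0.495 |
| 5% | 0.145 | 0.310 | 0.418 |

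**The case against.** The strongest reply is that the Follow-up Period text is written for exactly these subjects, those who stop drug before radiological progression, and it ends both imaging and markers at any other anticancer treatment. On that reading the troublesome scans are never scheduled. This is a fair reading, but the NOTE in 6.1 addresses the same subjects and requires the opposite after local treatment. The contradiction stands, and so does the missing ORR rule.

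The reply is right to limit several stronger inferences that a reader might draw:

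- *That assessments end only at systemic therapy.* They also end at radiological progression, and the follow-up text is broader.
- *That the permitted bone radiotherapy or small-mass removal can manufacture responders.* By Table 4, neither turns target SD into PR. Marker-only subjects have no documented lesion to treat. The residual path is a subject with no target lesion whose whole non-target disease is cleared, in a table headed for measurable disease.
- *That salvage surgery is a common route because the protocol's introduction cites it.* That text concerns relapse after initial chemotherapy. This trial requires disease not curable by surgery or chemotherapy, and much of its failure and late-relapse wording requires unresectable disease.
- *That the plan states such a response counts.* It follows from silence, not from a rule.

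Confirmation at 4 weeks or more in measurable disease also narrows the exposure. It does not close it, because shrinkage after radiotherapy, or a removed lesion, can persist to the confirming scan.

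**Conclusion.** The point holds as two linked defects: conflicting rules for ending assessments, and no cut at non-study anticancer treatment for best overall response, ORR, CBR or DOR, where PFS has one. Cases are likely to be few, and the documents do not allow their number to be estimated.

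The 21.6% and 17.1% should not be read as the trial's actual error rate. They assume one certain misclassified subject, and any other source of one false response would give the same figures. What they show is that this design cannot absorb even one such subject and keep its 10% control. The sample size and decision rules need no change. The sponsor should correct this, and the correction is inexpensive.

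**What to change.** - **SAP 5.1.1, 5.2.1 and 6.4.1.2.** Use only assessments on or before the start of the first non-study anticancer treatment (systemic therapy, antitumor radiotherapy or tumor resection) for best overall response, ORR and CBR. Keep subjects without a response by then in the denominator as non-responders.
- **SAP 5.2.2 and Table 2.** Censor DOR at the last assessment before that treatment, as Table 3 does for PFS.
- **Permitted local procedures.** State that a target-lesion response is not refused solely because permitted palliative bone radiotherapy or removal of a small non-measurable mass took place elsewhere. A blanket refusal could discard a genuine response in an untreated lesion and bias the ORR downward.
- **Assessment-stop wording.** Reconcile the systemic and any-treatment versions across the Protocol Synopsis, Table 1 footnotes, 2.2.1, 5.3.1.1, 5.3.1.3 and 6.1, and the SAP design section.

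The cost is wording in the SAP and protocol. Table 3 already needs the treatment dates, and SAP 6.2.4.5 already summarizes new anticancer therapy. The downside is a slightly lower ORR if such cases occur.
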